10. ETHICAL CONSIDERATIONS

10.1 Regulation statement

This study will be conducted according to the principles of the Declaration of Helsinki (version October 2013) and in accordance with the Medical Research Involving Human Subjects Act (WMO), the Medical Device Directive 93/42/EEC and Standard Operating Procedures (SOPs) of the UMC Utrecht.

10.2 Recruitment and consent

Adult patients qualifying for instrumented posterolateral spinal fusion of one or multiple levels in the thoracolumbar and lumbosacral region (T10-S2) with the use of autograft will be recruited by their treating orthopaedic surgeon or his/her clinical assistant. If the patient meets the in- and exclusion criteria and is willing to receive further information, he/she will be informed about the study and its objectives by a member of the study team authorized by the local principal investigator, and will be asked to participate. In addition to the oral information, the patient will get a written information letter (see document E1) and at least one week to discuss the study with others (including an independent physician) and consider their decision. After obtaining a written informed consent (see document E2), the patient will be enrolled in the study and will get a unique study identification-number according to which all obtained data will be registered. Informed consent will be recorded in the electronic patient dossier. The original signed informed consent form must be retained in the Investigator Site File; the patient will receive a copy.

10.3 Objection by minors or incapacitated subjects

Minors or incapacitated/incompetent subjects will not be recruited or enrolled in this study.

10.4 Benefits and risks assessment, group relatedness

Enrolled patients have the benefit of shorter surgery time and maintenance of iliac bone stock due to reduced bone harvesting from the iliac crest. The risk for a functional adverse outcome due to non-union with MagnetOs™ Granules is minimal, as the contralateral side will always be treated in the conventional way and both sides of the spine are instrumented. If MagnetOs™ Granules appears to perform inferior to the autograft condition, a one-sided functional posterolateral spinal fusion as a result of iliac crest bone, together with bilateral rigid instrumentation, is likely to compensate for this failure.

10.5 Compensation for injury

The sponsor has a liability insurance which is in accordance with article 7, subsection 6 of the WMO (see document G2). All participating centers have their own liability insurance. This is laid down in the clinical trial agreements.

The sponsor also has an insurance which is in accordance with the legal requirements in the Netherlands (Article 7 WMO). This insurance provides cover for damage to all research subjects through injury or death caused by the study (see document G1). The insurance applies to the damage that becomes apparent during the study or within 4 years after the end of the study.

11. ADMINISTRATIVE ASPECTS, MONITORING AND PUBLICATION

11.1 Handling and storage of data and documents

Data will be handled confidentially according to the Dutch Personal Data Protection Act. After obtaining a written informed consent, the patient will get a unique study identification-number (consisting of a hospital ID and consecutive number) according to which all data obtained for this study will be registered. Informed consent will be recorded in the electronic patient dossier. The original signed informed consent forms will be retained in the Investigator Site File, stored in a locked closet or room. The key to the study identification-numbers will be safeguarded by the local principal investigators.

All study data will be collected in Castor EDC and exported to SPSS for data analyses. The local study teams can enter the data directly in the web-based eCRF or after completing a printed version of the eCRF. Patients will receive an email via Castor EDC with a personalized link to the digital questionnaires. If patients prefer paper questionnaires, they should be completed at the outpatient clinic. To be able to reproduce the study findings and to help future users to understand and reuse the data, all changes made to the raw data and all steps taken in the analyses will be documented in queries, syntaxes or text documents.

Only the local study team authorized by the local principal investigator, the monitor and Health and Youth Care Inspectorate have access to the source data in the medical patient dossier; the principal investigator and coordinating investigator will only receive the completed CRFs and corresponding images, as well as the (S)AE-forms and relevant additional information.

At the UMC Utrecht, research data and files will be stored and archived on the research network disc of the division of Surgical Specialties.

All study data will be saved for at least 15 years after the end of the study.

11.2 Monitoring and Quality Assurance

The study will be monitored by trained and independent monitors from TFS, according to the guidelines of the Dutch Federation of University Medical Centers (NFU), adjusted to the UMC Utrecht. The purposes of monitoring are to verify that:

1. The rights and well-being of human subjects are protected;
2. The reported trial data are accurate, complete, and verifiable from source documents;

3. The conduct of the trial follows the currently approved protocol/amendment(s), with GCP, and with the applicable regulatory requirement(s).

The potential risks associated with participation in this study can be classified as 'negligible risk'. This is because the material (tricalcium phosphate TCP) is biochemically well characterized and applied for more than 30 years in millions of patients worldwide. The difference of this material is the microstructure which is more porous and therefore more bone inductive. A very similar material was investigated in the recently performed AxA study (METC nr 13-192) where no material related adverse events were reported. The risk of performing less good than autologous bone is mitigated by the bilateral (intrapatient) design, where for each fusion level always one side is treated with autologous bone and the other side with MagnetOs™ Granules. In addition the fusion is always instrumented with posterior fixation which immobilizes the segment and will cause a fusion in the long term. Therefore the addition of Magnetos on one side is fundamentally different from a standalone application and should be regarded as an augmentation to enhance fusion on that side while traditional fusion is achieved with autograft on the other side and the rigid fixation. This negligible risk is compensated with the definite advantage of less autologous bone graft donor side morbidity.

The following on-site monitoring strategy (per site) is proposed:

1. One initiation visit;
2. Three monitor visits;
3. One close-out visit.

More details on the monitoring strategy are given in document K6a.

11.3 Amendments

Amendments are changes made to the research after a favorable opinion by the accredited METC has been given. All amendments will be notified to the METC that gave a favourable opinion.

11.4 Annual progress report

The principal investigator/sponsor will submit a summary of the progress of the trial to the accredited METC once a year. Information will be provided on the date of inclusion of the first subject, numbers of subjects included and numbers of subjects that have completed the trial, serious adverse events, other problems, and amendments.

11.5 End of study report

The investigator will notify the accredited METC of the end of the study within a period of 8 weeks. The end of the study is defined as the last patient's last visit.

In case the study is ended prematurely, the investigator will notify the accredited METC within 15 days, including the reasons for the premature termination.

Within one year after the end of the study, the principal investigator/sponsor will submit a final study report with the results of the study, including any publications/abstracts of the study, to the accredited METC.

11.6 Public disclosure and publication policy

Kuros' participation in funding will be disclosed to any audience to which any information or results of this study are presented. The local principal investigators are permitted to present at symposia, national or regional professional meetings, and to publish in journals, theses or dissertations, or otherwise of their own choosing. Kuros will be provided with a manuscript of any proposed publication at least forty-five (45) days prior to submission, and with the abstract of any proposed presentation at conferences at least thirty (30) days prior to submission, in order to review any such manuscript and to request changes therein to protect inventions and/or proprietary rights and proprietary interests. See the agreement for more detailed information on disclosures and the publication policy.

12. STRUCTURED RISK ANALYSIS

12.1 Potential issues of concern

This study involves the application of a registered product (MagnetOs™ Granules) to be used within the indication and not in combination with other products.

12.2 Synthesis

As previously indicated, the main risk of this study will be inferior performance of MagnetOs™ Granules, resulting in a lower (unilateral) posterolateral fusion rate. Based on the preclinical studies as described in the Investigator's Brochure (see Chapter 6), this risk can be considered minimal. Furthermore, the most closely related and currently investigated MagnetOs™ Granules has shown to perform superior to currently widely applied competitor TCPs like Vitoss® and Actifuse®. To minimize risks, MagnetOs™ Granules will only be applied unilaterally in instrumented posterolateral spinal fusions. The contralateral side will receive autologous bone graft that is considered the gold standard for this surgical procedure. Furthermore, instrumentation will stabilize the spinal segments to allow an optimal environment for bony fusion. All patients may benefit from the study in terms of less surgery time and maintenance of iliac bone stock, since only half of the required bone graft will be harvested from the iliac crest. When MagnetOs™ Granules is indeed non-inferior to iliac crest bone graft, this harvesting procedure may be abandoned in future patient populations.

APPENDIX A. STATISTICAL ANALYSIS

The statistical methods were designed previously for the AxA trial in collaboration with a medical statistician, dr. [name] of the Julius Center, UMC Utrecht, the Netherlands.

Sample size calculation

The numeric results for a non-inferiority (one-sided) test of a difference are shown in the table below. Based on a 1:1 paired assignment of AttraX® Putty to the control condition with autograft, a power of 80%, a one-sided alpha of 0.05, a non-inferiority margin of 15%, an estimated fusion percentage of 50% for unilateral grafting and 70% concordance between both sides of the fusion trajectory, the required sample size for the primary outcome is 84 patients.

Definitions

- Power: probability of rejecting a false null hypothesis;
- N: number of subjects, sample size;
- De: maximum difference between the two proportions that is still called 'equivalent';
- Da: actual difference between Pt and Ps, i.e. Da = Pt-Ps;
- Pt: the response proportion to the treatment (experimental or new) test;
- Ps: the response proportion to the standard (reference or old) test;
- Nuisance Parameter: value that is needed, but is not a direct part of the hypothesis;
- Alpha: probability of rejecting a true null hypothesis;
- Beta: probability of accepting a false null hypothesis.

Power Analysis of Non-Inferiority Tests of Correlated Proportions

Page/Date/Time 19/4/2012 1:37:28 PM

Power	Sample	Equiv.	Actual	Treatment	Standard	Nuisance	Alpha	Beta
	Size (N)	Difference (De)	Difference (Da)	Proportion (Pt)	Proportion (Ps)	Parameter (P01+P10)		
130.10000-0.10000								
0.80005	5889	0.10000	-0.08000	0.42000	0.50000	0.30000	0.05000	0.19995
0.80003	1400	0.10000	-0.06000	0.44000	0.50000	0.30000	0.05000	0.19997
0.80024	591	0.10000	-0.04000	0.46000	0.50000	0.30000	0.05000	0.19976
0.80037	315	0.10000	-0.02000	0.48000	0.50000	0.30000	0.05000	0.19963
0.80135	191	0.10000	0.00000	0.50000	0.50000	0.30000	0.05000	0.19865
0.80000	24761	0.11000	-0.10000	0.40000	0.50000	0.30000	0.05000	0.20000
0.80009	2623	0.11000	-0.08000	0.42000	0.50000	0.30000	0.05000	0.19991
0.80024	899	0.11000	-0.06000	0.44000	0.50000	0.30000	0.05000	0.19976
0.80050	436	0.11000	-0.04000	0.46000	0.50000	0.30000	0.05000	0.19950
0.80053	250	0.11000	-0.02000	0.48000	0.50000	0.30000	0.05000	0.19947
0.80009	158	0.11000	0.00000	0.50000	0.50000	0.30000	0.05000	0.19991
0.80005	6202	0.12000	-0.10000	0.40000	0.50000	0.30000	0.05000	0.19995
0.80006	1479	0.12000	-0.08000	0.42000	0.50000	0.30000	0.05000	0.19994
0.80009	626	0.12000	-0.06000	0.44000	0.50000	0.30000	0.05000	0.19991
0.80044	335	0.12000	-0.04000	0.46000	0.50000	0.30000	0.05000	0.19956
0.80164	204	0.12000	-0.02000	0.48000	0.50000	0.30000	0.05000	0.19836
0.80170	134	0.12000	0.00000	0.50000	0.50000	0.30000	0.05000	0.19830
0.80009	2763	0.13000	-0.10000	0.40000	0.50000	0.30000	0.05000	0.19991
0.80032	950	0.13000	-0.08000	0.42000	0.50000	0.30000	0.05000	0.19968
0.80046	462	0.13000	-0.06000	0.44000	0.50000	0.30000	0.05000	0.19954
0.80079	266	0.13000	-0.04000	0.46000	0.50000	0.30000	0.05000	0.19921
0.80094	169	0.13000	-0.02000	0.48000	0.50000	0.30000	0.05000	0.19906
0.80255	115	0.13000	0.00000	0.50000	0.50000	0.30000	0.05000	0.19745
0.80000	1558	0.14000	-0.10000	0.40000	0.50000	0.30000	0.05000	0.20000
0.80039	662	0.14000	-0.08000	0.42000	0.50000	0.30000	0.05000	0.19961
0.80043	355	0.14000	-0.06000	0.44000	0.50000	0.30000	0.05000	0.19957
0.80021	216	0.14000	-0.04000	0.46000	0.50000	0.30000	0.05000	0.19979
0.80181	143	0.14000	-0.02000	0.48000	0.50000	0.30000	0.05000	0.19819
0.80338	96	0.14000	0.00000	0.50000	0.50000	0.30000	0.05000	0.19662
0.80029	1001	0.15000	-0.10000	0.40000	0.50000	0.30000	0.05000	0.19971
0.80033	488	0.15000	-0.08000	0.42000	0.50000	0.30000	0.05000	0.19967
0.80093	282	0.15000	-0.06000	0.44000	0.50000	0.30000	0.05000	0.19907
0.80163	180	0.15000	-0.04000	0.46000	0.50000	0.30000	0.05000	0.19837
0.80062	122	0.15000	-0.02000	0.48000	0.50000	0.30000	0.05000	0.19938
0.80098	84	0.15000	0.00000	0.50000	0.50000	0.30000	0.05000	0.19902
0.80005	697	0.16000	-0.10000	0.40000	0.50000	0.30000	0.05000	0.19995
0.80031	375	0.16000	-0.08000	0.42000	0.50000	0.30000	0.05000	0.19969
0.80039	229	0.16000	-0.06000	0.44000	0.50000	0.30000	0.05000	0.19961
0.80183	152	0.16000	-0.04000	0.46000	0.50000	0.30000	0.05000	0.19817
0.80168	106	0.16000	-0.02000	0.48000	0.50000	0.30000	0.05000	0.19832
0.80386	75	0.16000	0.00000	0.50000	0.50000	0.30000	0.05000	0.19614
0.80009	514	0.17000	-0.10000	0.40000	0.50000	0.30000	0.05000	0.19991
0.80095	298	0.17000	-0.08000	0.42000	0.50000	0.30000	0.05000	0.19905
0.80029	190	0.17000	-0.06000	0.44000	0.50000	0.30000	0.05000	0.19971
0.80159	130	0.17000	-0.04000	0.46000	0.50000	0.30000	0.05000	0.19841
0.80146	84	0.17000	-0.02000	0.48000	0.50000	0.30000	0.05000	0.19854
0.80249	66	0.17000	0.00000	0.50000	0.50000	0.30000	0.05000	0.19751

Primary analysis

The CT score will be dichotomized into fused and not fused. To allow the inclusion of patients with intended fusion of multiple segments, the sum of fusions on each side of the spine of these patients will be compared. If one side of a fusion-level is considered not evaluable, this will be excluded as well as the contralateral level. In multilevel patients, superiority (in number of fused levels) of one side, will be considered fusion and the other side non-fusion to prevent an unequal influence of patients with multi-level fusions. Although fusion assessment by this method gives more a "relative performance score" than a "fusion rate," analyzing the fusion rate of individual levels will not be adequate. There is strong reason to believe that the fusion rate will vary from patient to patient, so the fusion of individual vertebrae from one patient will not be independent. Since the study is randomized, this dependence should have no effect on a point estimate for the difference in fusion rates for MagnetOsTM Granules vs. autograft, but will certainly affect the standard error of the difference, thereby making standard statistical inference unreliable.

Although we know of no way of generating correct p-values or confidence intervals for differences in fusion rates using clustered data, it is possible to use a multi-level model (in which the clustering of vertebrae within patients is taken into account) to examine the effect of MagnetOsTM Granules and autograft on fusion, and using the vertebrae as the primary level of analysis. Such a model will produce an odds ratio instead of a difference in fusion rates. Since a sample size calculation based on a multi-level analysis requires a number of assumptions that cannot be supported by current data, we decided to perform sample size calculation based on the McNemar's test, and to use the multi-level model as a secondary analysis since it will make better use of the complete data while correctly taking the clustering into account.

Secondary Analysis

A three-level generalized estimating equations (GEE) model will be used to examine fusion on each side of a vertebra, while accounting for clustering of measurements (fusion on each side of the spine) within spinal levels and within patients. The GEE model will use compound symmetry working correlation matrices for correlation of measurements within vertebrae and vertebrae within patients. In this model, the presence of interbody fusion can also be incorporated as a separate factor. The outcome will be fusion (yes/no) and the explanatory variable will be the treatment condition. Analysis will result in an odds ratio for MagnetOsTM Granules vs. autograft and a 95% confidence interval.

References

1. Lewis, J.A., *Statistical principles for clinical trials (ICH E9) an introductory note on an international guideline*. Statistics in Medicine, 1999. **18**(15), p. 1903-42.
2. Liu, J., et al., *Tests for equivalence or non-inferiority for paired binary data*. Statistics in Medicine, 2002. **21**(2), p. 231-45.
3. Nam, J., *Establishing equivalence of two treatments and sample size requirements in matched-pairs design*. Biometrics, 1997. **53**, p. 1422-30.
4. Nam, J. and Blackwelder, W.C., *Analysis of the ratio of marginal probabilities in a matched-pair setting*. Statistics in Medicine, 2002. **21**(5), p. 689-99.

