Adult patients qualifying for instrumented posterolateral spinal fusion of one to six levels in the thoracolumbar and lumbosacral region (T10-S2) with the use of autograft will be recruited by their treating orthopaedic surgeon or his/her assistant. After obtaining informed consent, they will be operated locally according to normal planning and the surgical techniques suggested in Appendix B. Per-operatively, after instrumentation of the spine and preparation of the bilateral trajectory for grafting, the randomized allocation of the graft type (left or right) will be disclosed. So in each patient, each side of the fusion trajectory will be one of the two conditions: the **autograft condition**, a combination of local bone obtained from decompression and/or preparation for fusion (facetectomy and denudement), supplemented with at least 50% corticocancellous bone harvested from the iliac crest, or the **MagnetOs condition**. Allocation of the conditions will always be to only one side of the spine, also when multiple levels are incorporated. Corticocancellous bone will be taken from only one iliac wing at the side of the autograft condition, unless this side is inappropriate due to previous harvesting or anatomical reasons. If possible, harvesting is done via the same posterior incision for spinal fusion. In case of an additional interbody fusion procedure, the cage is preferably filled with local autograft bone and positioned before opening of the randomization envelope. If the surgeon decides to use iliac crest bone for this device, the cage can only be inserted after the randomization and related harvesting side has been disclosed. All patients will be evaluated radiologically and clinically at several time points pre- and postoperatively (see Figure 3.1), and all (serious) adverse events that in any way may be related to the procedure will be carefully documented and evaluated to meet the objectives described in Chapter 2.

The expected duration of the study is approximately 4 years from the commencement of patient enrollment; enrollment is expected to take two years, followed by two years follow-up. After completion of one-year follow-up, the analysis for the primary outcomes will be done by the investigators at the UMC Utrecht.

[figure not shown]

Figure 3.1: Schematic overview of study design.

Rationale for intra-patient design

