4.2 Inclusion criteria

In order to be eligible to participate in this study, a patient must meet all of the following criteria:

- To be treated with instrumented posterolateral thoracolumbar spinal fusion with the use of iliac crest bone, with or without additional posteriorly inserted interbody devices (PLIF, TLIF), because of (1) deformity, (2) structural instability and/or (3) expected instability as a result of decompression for spinal stenosis;
 1. Deformity is defined as a scoliosis in the coronal plane of $>20^\circ$ and/or a sagittal balance disturbance according the SRS/Schwab classification³³ on standardized standing full spine radiographs;
 2. Preoperative instability is defined as a progressive angular deformity or spondylolisthesis in standing radiographs;
 3. Decompression for spinal stenosis is done in the occurrence of radiological evidence of stenosis on MRI and clinical leg and/or back pain with one or more of the following phenomena: radiculopathy, sensory deficit, motor weakness, reflex pathology or neurogenic claudication.
- Non-responsive to at least 6 months of non-operative treatment prior to study enrollment;
- Fusion indicated for one to six levels in the T10 to S2 region. In case of vertebral osteotomies (PSO or VCR) the osteotomized segment will not be included in the assessment of the fusion rate;
- Willing and able to understand and sign the study specific Patient Informed Consent;
- Skeletally mature between 18 and 80 years of age.

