4.4 Sample size calculation

The primary objective of this study is to demonstrate that treatment with MagnetOsTM Granules is non-inferior to autograft to obtain bony fusion in the spine. The primary outcome is the rate of successful posterolateral bony fusion after one year, assessed at CT-scans. Fusion will be scored binomially and non-inferiority of fusion in the MagnetOs condition will be assessed using a McNemar's test.

Based on literature^{6,28-30,34} and the preliminary results of the AxA study, we estimate a fusion percentage of 50% for unilateral grafting after one year, and a 70% concordance between the left and right side of the fusion trajectory (i.e. both sides fused or non-fused). The non-

inferiority margin is set at an absolute 15% less effectiveness in the MagnetOs condition after one year, which corresponds with 15% less posterolateral sides that are judged as fused. In other words, the rate of fused posterolateral sides in the MagnetOs condition should be more than 35% if the autograft condition shows 50% fusion. We argued that the percentage of the iliac crest graft related complications, ranging from 5% major complications to 40% minor complications, may justify 15% less fusion in a condition that eliminates these complications.

Based on a 1:1 paired assignment of MagnetOsTM Granules to the control condition with autograft, a power of 80%, a one-sided alpha of 0.05 and the non-inferiority margin of 15%, the required sample size for the primary outcome is 84 patients (see Appendix A). We assume that approximately 15% of the included patients will not be evaluable after one year. The intra-patient analyses are not possible when the fusion area has to be revised or when a deep wound infection has occurred and considerable amounts of graft material have to be removed (expected percentage 2-5%). Other failures are lost to follow-up or bad scan quality. Therefore, the total number of patients to be enrolled will be 100.

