9.1 Primary efficacy analysis

For the primary efficacy analysis, a comparison will be made between the fusion performance of the MagnetOsTM condition and the autograft condition, scored from the one-year (12-15 months) CT-scans according to the method described in Appendix C. Patients that required revision surgery influencing the fusion will be excluded from this analysis. In addition, if one side of a fusion-level is considered not evaluable, this level will be excluded. All evaluable scores will be dichotomized into fusion and no fusion. To allow inclusion of patients with fusion of multiple segments, without increasing the influence of these patients on the outcome, each side in these patients will be statistically considered as one condition. This means that the possible outcomes in these patients are: no fusion (if none of the levels is fused), equal fusion (if an equal number of segments is fused per side) or fusion at one side vs. no-fusion at the other side in case one side contains more fused segments than the other side.

The basis for the primary efficacy analysis will be the test of non-inferiority by performing a McNemar's test. The null hypothesis is that inferiority in fusion rate of the MagnetOsTM Granules compared to the autograft condition is greater than 15% (PAG-PMAG \geq 15%); the alternative hypothesis is that the MagnetOsTM Granules fusion rate will not be lower than the autograft success rate by more than 15% (PAG-PMAG< 15%).

In addition to the McNemar's test, a generalized estimating equations (GEE) model will be used to examine fusion on each side of a vertebra, while accounting for clustering of vertebrae within patients. The outcome will be fusion (yes/no) and the explanatory variable will be treatment. Analysis will result in an odds ratio for MagnetOsTM Granules vs. autograft and a 95% confidence interval.

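### The null hypothesis and 15-point margin are stated as a fusion-rate difference, but in multilevel patients the primary test only asks which side fused more levels

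*Combined protocol and SAP*

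**What the plan says.** Section 4.2 admits multilevel patients: "Fusion indicated for one to six levels in the T10 to S2 region". Section 3 fixes the layout: "Allocation of the conditions will always be to only one side of the spine, also when multiple levels are incorporated".

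The margin in 4.4 is an absolute 15%, "which corresponds with 15% less posterolateral sides that are judged as fused", with the example that MagnetOs must exceed 35% if autograft reaches 50%. It is justified by trading less fusion against donor-site complications. Section 9.1 takes as null hypothesis that "inferiority in fusion rate of the MagnetOsTM Granules compared to the autograft condition is greater than 15" percent.

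The variable that enters the test is different. For multilevel patients 9.1 allows no fusion, equal fusion, or "fusion at one side vs. no-fusion at the other side in case one side contains more fused segments than the other side". Appendix A (Primary analysis) gives the same rule, "superiority (in number of fused levels) of one side, will be considered fusion and the other side non-fusion", and says openly that the result is closer to a relative performance score than to a fusion rate. Its reasons are that levels within a patient are dependent, that multilevel patients should not weigh more, and a technical obstacle: "Although we know of no way of generating correct p-values or confidence intervals for differences in fusion rates using clustered data". A generalized estimating equations (GEE) model on the levels is added. It yields an odds ratio with a 95% interval and no margin.

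**The concern.** Under the rule, a side with 4 of 5 levels fused is non-fusion if the other side has 5 of 5, and a side with 1 of 5 is fusion if the other has none. A side's code depends on the opposite side, so the coded proportions are not fusion rates in multilevel patients. The score also ignores the size of a lead: in two three-level patients, a 3-0 loss and a 1-0 win cancel, although the mean difference in levels fused is (-1 + 1/3)/2 = -33 points.

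At stake is the wording of the primary conclusion. It would read as a fusion rate within 15 points of autograft, which the test did not examine. A graft inside that limit can fail and, less plausibly, one at the limit can pass too often.

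Section 9.3 reuses the method for the two-year comparison. The score codes 1/3 against 1/3 and 3/3 against 3/3 alike as equal fusion, so it cannot show fusion increasing from one year to two, which is that objective. The GEE's explanatory variable is treatment, so its odds ratio compares grafts, not years.

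**Working it through.** **Terms.** A loss is a patient whose autograft side fused more levels; a win is one whose MagnetOs side did. Discordance is P(loss) + P(win). The score deficit is P(loss) - P(win). L is the number of levels.

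**Inputs from 4.4 and Appendix A.** Margin δ = 0.15, one-sided alpha 0.05, true difference 0, concordance 70% (discordance 0.30), N = 84. The documents do not give the mix of levels, so every mix below is an assumption.

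**1. The plan's own figure.** The normal approximation gives (1.645 + 0.842)² × 0.30 / 0.15² = 82.4, so 83. The exact check uses the matched-pairs score test. With b losses and c wins among n patients, Z = [(c - b)/n + δ] / √[(2q + δ - δ²)/n], where q is the positive root of -2n·q² + [c(1 - 3δ) + b(1 - δ) - 2(n - b - c)δ]·q + cδ(1 - δ) = 0. Summing multinomial probabilities over Z ≥ 1.645 at n = 84 gives 0.80098, identical to the Appendix A table.

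**2. Stricter direction.** By simple arithmetic: with three levels, losses by one level in 30% of patients and wins by one level in 10%, the score deficit is 20 points but the per-level deficit is 0.20/3 = 6.7 points. An assumed logistic model with a patient effect, calibrated to 70% concordance at one level, gives:

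| Levels | Score deficit when levels fuse at 50% vs 35% | Per-level deficit equal to 15 score points |
|---|---|---|
| 1 | 15.0 | 15.0 |
| 2 | 23.9 | 9.3 |
| 3 | 30.5 | 7.2 |
| 4 | 35.7 | 6.1 |
| 6 | 44.0 | 4.8 |

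A latent-normal model that varies how closely levels on one side agree gives 8.7 to 13.1 points (two levels) and 6.7 to 12.4 (three) for the last column. It returns to 15 only in the limit where all levels on a side agree.

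**3. Liberal direction (constructed).** Every loss is at all L levels and every win is by one level. A per-level deficit of exactly 15 points means P(loss) - P(win)/L = 0.15, with P(loss) + P(win) = 0.30. Hence P(loss) = (0.15 + 0.30/L)/(1 + 1/L).

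| Levels (all patients) | Loss / win | Score deficit | Exact P(pass), N = 84 |
|---|---|---|---|
| 1 | 0.225 / 0.075 | 15.0 | 5.0% |
| 2 | 0.200 / 0.100 | 10.0 | 21.1% |
| 3 | 0.1875 / 0.1125 | 7.5 | 34.9% (0.3485) |
| 6 | 0.1714 / 0.1286 | 4.3 | 55.5% |

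Under three assumed mixes of one to six levels (60/30/10/0/0/0, 35/30/20/10/3/2 and 15/25/25/20/10/5 percent) the same pattern passes with probability 10%, 18% and 29% if each level group has a 15-point deficit at 30% discordance. It is 9%, 16% and 26% if all groups share one loss and one win probability.

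There is a limit to this. At score difference 0 the per-level deficit in this pattern is (discordance/2)(1 - 1/L). At 30% discordance that is 10 points for three levels and 12.5 for six, both inside the margin.

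**4. Power.** At N = 84 with true score difference 0, exact power is 80.1% at 30% score discordance, and 75%, 70%, 66%, 62% and 58% at 35%, 40%, 45%, 50% and 55%.

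**5. The missing interval.** Each graft fills one whole side, so each patient yields one difference in proportion of levels fused. Patients are independent, so an ordinary one-sample interval for the mean difference is available without modelling dependence between levels.

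**The case against.** The strongest reply is that 9.1 treats each side of a multilevel patient as one condition just before it writes the hypothesis, and that 4.4 speaks of sides, not levels. The hypothesis could then be read as a difference in sides coded fused. On that reading the test is valid for its own score, and the 15-point per-level benchmark is the reviewer's. This stands in part: the test is valid for the score, the coding is disclosed and reasoned, and one-level patients are unaffected. It does not rescue the wording. The example of 35% against 50% and the trade against donor-site complications concern how much fusion is lost, and nothing explains why 15 points of net losses is acceptable on the same grounds.

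A reader might infer that the test is liberal and that a pass would probably be false. The documents do not support that. Under symmetric or uniform effects the test is stricter, and the 21% to 56% figures need an extreme pattern and the same number of levels in every patient.

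A reader might also infer that the trial is underpowered. Section 4.4 assumes "a 70% concordance between the left and right side of the fusion trajectory (i.e. both sides fused or non-fused". Section 3 uses fusion trajectory for the whole side, so 70% reads as per patient, and 9.1 already makes unequal partial counts discordant. The 80% therefore stands at its stated input; step 4 shows only its sensitivity.

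The GEE does use every level and is a useful check, but without a margin it cannot decide non-inferiority.

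**Conclusion.** The point holds, and the text is wrong as written: hypothesis and margin are on one scale and, in multilevel patients, the test is on another. A pass does not by itself bound the fusion-rate difference, and a failure does not show that the difference exceeds 15 points. The two coincide for one-level patients, so the size depends on the share of multilevel patients, which is not stated. The figures in both directions rest on assumed models, patterns and mixes. They show that the two scales do not map one to one; they are not forecasts of error rates in this trial. Because the score is disclosed, valid for itself, often the stricter test and accompanied by a level-based analysis, this is a point that should be fixed rather than one that invalidates the trial. The two-year point stands without assumptions.

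**What to change.** Amend 4.4, 9.1, 9.3 and Appendix A before the blinded CT readings are linked to allocation.

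1. Minimum: restate the null hypothesis on the relative-score scale (net share of patients whose autograft side fused more levels), justify 15 points there, and do not report the result as a fusion-rate difference.
2. In addition, prespecify for each patient (evaluable levels fused on the MagnetOs side minus those on the autograft side) / evaluable levels. Weight patients equally, and report the mean with a one-sided 95% lower bound beside the score test. Choose a bound whose size has been checked. With one-level patients at N = 84 and 16%, 20%, 25% and 30% discordance, a plain t bound has size 8.5%, 6.3%, 5.2% and 5.0%, and Hall's skewness-corrected t 3.0%, 4.8%, 5.1% and 5.0%. In the constructed patterns at 30% to 50% discordance the plain t has 5.8% to 7.5% and Hall's 4.2% to 4.8%. In mixed-level symmetric models the two are similar (5.0% to 5.5% and 5.1% to 5.5%). Making this measure primary is an option only if the 15-point margin is justified for the proportion of levels fused, because 4.4 argues it for sides.
3. For two years, report the proportion of levels fused per side at each year, and state how patients without a two-year CT are counted.

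Cost: one amendment notified to the ethics committee (11.3), a margin rationale, and a documented check of the bound. The CT readings are the same, with no extra patients or scans. Items 1 and 2 keep the score that Appendix A took over from AxA; only a change of primary variable would depart from it.
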